## Appendix 4 Unscheduled Safety Assessment Visits, Post-Study Treatment Discontinuation Visits, or Post-Explantation Safety Visits

The assessments listed below will be performed at:

- Unscheduled safety assessment visits
- Study visits for patients who discontinued study treatment but remain in the study. Other assessments, listed in Appendix 1 and Appendix 2 for specific study visits, may be performed at discretion of the investigator.
- Safety visits following explantation (at 1, 7 [ $\pm$  2], 30 [ $\pm$  7], and 60 [ $\pm$  7] days post-explantation).

Assessments a,b			
Vital signs (blood pressure and pulse)	x		
BCVA (assessed on ETDRS chart at a 4-meter starting distance) $^{\circ}$	х		
Slitlamp examination	x		
Dilated binocular indirect high-magnification ophthalmoscopy	x		
IOP d	x		
SD-OCT °	х		
Adverse events f	х		
Concurrent ocular procedures	x		
Concomitant medications	x		

BCVA = best-corrected visual acuity; ETDRS=Early Treatment Diabetic Retinopathy Study; IOP = intraocular pressure; SD-OCT = spectral-domain optical coherence tomography.

- a An unscheduled safety assessment visit is applicable to any randomized study patients. If an unscheduled safety assessment visit is determined to be necessary by the physician, perform all listed assessments. Ocular assessments may be performed on one eye only, except for BCVA that must be performed on both eyes.
- b At a post-study treatment discontinuation visit or a post-explantation safety visit, perform all listed assessments. Ocular assessments may be performed on the study eye only, except for BCVA which must be performed on both eyes.
- c BCVA assessment must be performed in both eyes by masked visual acuity examiner. Perform fingercounting test followed by hand motion and light perception tests when necessary.
- d The method used for the IOP measurement for a patient must remain consistent throughout the study.
- e Refer to the reading center manual for details.
- f Adverse event causality to be evaluated by the qualified ophthalmologist.

## Appendix 5 Additional Assessments if Supplemental Treatment Criteria Are Met

If a patient in the implant arm meets the supplemental treatment criteria (see Section 5.1.5.3 at any of the following weeks (Weeks 16, 20, 40, 44, 64, 68, 88, and 92 and Weeks 112 and 116 for patients who follow an alternate final study visit scenario), the following assessments must be performed in addition to assessments listed in Appendix 1.

Assessments			
Pregnancy test a	х		
Serum PK sample b	x °		
Aqueous humor PD sample b	x °		
Plasma and serum PD sample	x °		
Optional pre- and post-study treatment antimicrobials	х		
Supplemental intravitreal ranibizumab 0.5 mg	х		
Post-treatment finger-counting test d	х		
Follow-up call e	x		

IxRS = interactive voice or web-based response system; PD = pharmacodynamic; PK = pharmacokinetic.

- a For women of childbearing potential, including those who have had tubal ligation, urine pregnancy test will be performed locally prior to supplemental treatment. If a urine pregnancy test is positive, it must be confirmed by a serum pregnancy test. Do not administer the supplemental treatment until the final results are available. If the serum pregnancy test is positive, do not administer the supplemental treatment.
- b Collect sample prior to supplemental intravitreal injection.
- c Sample should be collected at the supplemental treatment visit and at the subsequent study visit.
- d Finger-counting test, followed by hand motion and light perception tests (when necessary) performed by the physician within 15 minutes post-treatment for the study eye only. Patients will be allowed to leave the office after the designated physician has assessed that there are no safety concerns. If any safety concerns or immediate toxicity are noted, the patient will remain at the office and will be treated according to the designated physician's clinical judgment. If applicable, the adverse event and treatment of adverse event (if applicable) will be reported.
- e Patients will be contacted 3 (± 1) days following supplemental treatment to elicit reports of any decreases in vision, occurrence of eye pain, unusual redness, or any other new ocular symptoms. Patients will also be asked whether they have taken the prescribed, self-administered, post-treatment antimicrobials.

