### Figure 1 Study Schema

D = day; Rd = randomization.

- a Patients in the implant arm may be eligible for supplemental treatment with intravitreal ranibizumab 0.5 mg at Weeks 16, 20, 40, 44, 64, 68, 88, and 92.
- b At Week 96, patients may consent to enter the open-label extension study GR40549 (Portal). In the event a patient is unable to complete Archway at Week 96 and enroll in Portal on the same day, follow the alternate scenarios presented in Table 3 and the schedules of activities in Appendix 1, Table 3 and Appendix 2, Table 3.

**Port Delivery System with Ranibizumab—F. Hoffmann-La Roche Ltd.** 36/Protocol GR40548, Version 5
Patients must satisfy all eligibility criteria at both the screening and the randomization visits, including receipt of all screening visit images by the central reading center. Historical optical coherence tomography (OCT) images taken around the time of diagnosis of nAMD will be evaluated by the central reading center to support determination of a patient's eligibility.

If available, fluorescein angiography (FA) images taken around the time of diagnosis of nAMD in the study eye should be submitted to the central reading center but will not be required to determine eligibility at the screening visit.

As part of the screening process, the central reading center will evaluate the patient's FA, fundus photography (FP), fundus autofluorescence (FAF), and spectral-domain optical coherence tomography (SD-OCT) images obtained at the screening visit, as well as the patient's historical OCT (mandatory) and historical FA images (if available) taken around the time of nAMD diagnosis to provide an objective, masked assessment of patient eligibility regarding CNV lesion details (including macular atrophy). Screening visit assessments may be performed on multiple days but must be completed within 7 days of obtaining informed consent.

Patients who do not meet eligibility criteria (screen-failed patients) may be eligible to repeat screening up to two times if deemed appropriate by the investigator. At rescreening, a new screening number will be assigned to the patient through an interactive voice or web-based response system (IxRS) and all screening visit assessments will be performed except for FA image collection if reading center–accepted images were taken within 12 weeks from the rescreening visit.

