The Sponsor will require that the following steps be implemented as a best attempt to mask VA examiners in order to minimize biases in VA assessments.

- The VA examiner will only conduct refraction and VA assessments and will be masked as best as possible to patient study eye assignment, study visit type, and patient treatment assignment.
- The VA examiner will have no access to a patient's BCVA scores from previous visits and will be aware only of the patient's refraction data from previous visits.
- The VA examiner may provide no other direct or indirect patient care.
- Patients and unmasked site personnel will be asked not to discuss the study eye assignment, study visit type, and patient treatment assignment with the VA examiner.

At the Archway Week 96, eligible patients may consent to enter the open-label extension Study GR40549 (Portal), designed to evaluate the long-term safety and tolerability of PDS, and receive treatment according to the extension study protocol. The Portal enrollment visit will occur the same day as Archway Week 96 visit for both arms (Table 3). Eligible patients who do not consent to enter the Portal study should complete the Archway Week 96 procedures as described in Appendix 1 or Appendix 2, as applicable. In the event that an eligible patient in the implant arm decides not to enter Portal, the patient will be instructed to contact their study physician or the Sponsor's adverse event reporting line if they experience an adverse event related to the implant. Patients must contact their study physician if they elect to remove the implant. In order to provide flexibility due to extenuating circumstances and assure appropriate patient care, if the patient is unable to complete Archway at Week 96 and enroll into Portal during the same visit, several alternate final study visit scenarios are available (Table 3). In general, Archway patients should be provided the opportunity to remain on study and receive treatment at regular intervals until consenting patients can enroll into Portal per-protocol.

	IMPLANT ARM a				
	Scenario	Week 96 (± 7 days)	Monthly Week (X) (± 7 days)	Portal Enrollment Visit	
	Week 96 and Portal enrollment visits can be conducted within window.	Conduct the Week 96 visit.	Not Applicable	Conduct the Portal enrollment visit on the same day as the Week 96 visit. Administer the PDS refill-exchange (per Portal protocol).	
	IMPLANT ARM / Alternate Scenarios b				

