1	Week 96 visit can be conducted within window; Portal enrollment can only be conducted 21-28 days post-Week 96 visit.	Conduct the Week 96 visit; however do not administer a PDS-refill-exchange.	Conduct one Week (X) visit after Week 96 (i.e., Week 100).	Conduct the Portal Enrollment visit on the same day as Week 100 visit. Administer the PDS refill-exchange (per Portal protocol).	
2	Week 96 visit can be conducted within window; Portal enrollment visit is NOT expected to be conducted 21-28 days post- Week 96 visit.	Conduct the Week 96 visit and administer a PDS refill-exchange.	Conduct monthly Week (X) visits after Week 96 until the Portal Enrollment visit can be scheduled within the required window.	Conduct the Portal Enrollment on the same day as the final Week (X) visit. Administer the PDS refill-exchange (per Portal protocol).	
3	. Week 96 visit is missed.	Not applicable	Conduct a Week (X) visit and administer a PDS refill-exchange c . Conduct monthly Week (X) visits until the Portal Enrollment visit can be scheduled within the required window.	Conduct the Portal Enrollment visit on the same day as the final Week (X) visit. Administer the PDS refill-exchange (per Portal protocol).	

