# 5.1.5.3 Supplemental Treatment with Intravitreal Ranibizumab for Implant Patients

Patients randomized to the implant arm will be eligible for supplemental treatment with ranibizumab (0.5 mg intravitreal injections of 10-mg/mL formulation) at Weeks 16 and 20 (after implant insertion) and at Weeks 40, 44, 64, 68, 88, and 92 if any of the following criteria are met in the study eye:

• Decrease of ≥15 letters from the best-recorded BCVA in the study, due to nAMD disease activity

• Increase of  $\ge$  150  $\mu$ m in central subfield thickness (CST) on SD-OCT from the lowest CST measurement in the study, due to nAMD disease activity

• Increase of  $\geq$  100  $\mu$ m in CST on SD-OCT from the lowest CST measurement in the study associated with a decrease of  $\geq$  10 letters from the best recorded BCVA during the study, due to nAMD disease activity

At each visit in which supplemental treatment is possible, the study eye BCVA score and CST value must be entered into IxRS to assess the need for supplemental treatment. If any of the criteria above are met, the supplemental treatment must be administered at the end of the visit. If treatment cannot be administered at the end of the visit, patients will be asked to return within 7 days to receive supplemental treatment.

Following supplemental treatment with intravitreal ranibizumab 0.5 mg, patients will continue with scheduled implant refill-exchanges at Weeks 24, 48, and 72 relative to the Day 1 visit.

Note: Supplemental treatment is allowed at Weeks 16 and 20 (after implant insertion) and at Weeks 40, 44, 64, 68, 88 and 92 only if any of the criteria *listed* above are met. Supplemental treatment is not allowed at any other study visits. Patients with progressive worsening of nAMD disease activity (e.g., BCVA or CST worsening, new macular hemorrhage) who, in the investigator's judgment, require any treatment for nAMD in the study eye outside of protocol (e.g., ranibizumab intravitreal injection treatment at Week 8) will be discontinued from study treatment (i.e., no additional refill-exchanges) after discussion with the Medical Monitor. Patients discontinuing study treatment will be encouraged to attend as many scheduled study visits as possible, with an emphasis on completing the Week 36, Week 40, and Week 96 visits (see Appendix 4 for the minimum required assessments to be performed).

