#### Table 2: Implant Arm, Year 2, Early Study Termination and Explantation Visits, Footnotes (cont.)

z Patients will be scheduled for safety visits at 1, 7 ( $\pm$  2), 30 ( $\pm$  7), and 60 ( $\pm$  7) days post-explanation (refer to Appendix 4 for visit assessments).

- aa Implant photographs can be taken either the day of the explantation surgery (if possible) or within days leading to the explantation surgery.
- bb Samples can be taken either the day of the explantation surgery (if possible) or within days leading to the explantation surgery. Aqueous humor, plasma, and serum samples for biomarkers should all be taken at the same visit.
- cc If a patient is unable to complete Archway at Week 96 and enroll in Portal on the same day, follow the alternate schedule of activities in Appendix 1, Table 3.

Table 3:	Alternate Scenarios for Implant Arm: Week 96 and Week (X)
	(Q4W)

Assessment		Visit
	Week 96	Week (X) (Q4W)
Visit window (days)		±7
Contact IxRS a	x	x
Vital signs b	x	x c
Concomitant medications d	x	x
Adverse events e	x	x
Concurrent ocular procedures f	x	x
Pregnancy test g	x	x
Serum PK sample h	x	x
Serum ADA sample h	x	x
BCVA	х	x
IOP i	х	x
Slitlamp examination	x	x
Dilated binocular Indirect ophthalmoscopy j	x	x
SD-OCT k	x	x
Fundus photography k	х	x I, m
Fluorescein angiograph k	х	X I, m
Fundus autofluorescence k	х	X I, m
Lens photograph (fundus reflex photograph) k	x	x I, m
OCT-A (at selected sites) n	х	x I, m
Implant refill-exchange and video	x °	x p
Pre-and post-study treatment antimicrobials q	х	x
Post-treatment finger-counting test r	х	x
Implant photographs s	х	x t
Supplemental ranibizumab (if supplemental treatment criteria are met)		x u
Follow-up call v	x	x
Aqueous humor sample for biomarkers and ranibizumab conc. (optional)	x w	x w, x
Plasma and serum sample for biomarkers (if aqueous humor sample collected) (optional)	x w	X w, x

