## Table 3:Alternate Scenarios for Implant Arm: Week 96 and Week (X)
(Q4W), Footnotes (cont.)

- If Implant refill-exchange is administered. Finger-counting test, followed by hand motion and light perception tests (when necessary) performed by the physician within 15 minutes post-treatment for the study eye only. The patient will be allowed to leave the office after the designated physician has assessed that there are no safety concerns. If any safety concerns or immediate toxicity are noted, the patient will remain at the office and will be treated according to the designated physician's clinical judgment. If applicable, the adverse event will be reported.
- s In addition to the timepoints listed, the photograph will also be taken at any visit if there are concerns with Implant function.
- t If Implant refill-exchange is administered and at the last Week (X) of the study.
- u Only for patients who will reach Week 112 and 116. For additional required assessments if supplemental treatment criteria are met see Appendix 5.
- v If study treatment is administered. All study patients will be contacted 3 (± 1) days following study treatment to elicit reports of any decreases in vision, occurrence of eye pain, unusual redness, or any other new ocular symptoms. Patients will also be asked whether they have taken the prescribed, self-administered, post-treatment antimicrobials.
- w If a patient has consented to this optional sample collection, collect if implant refill-exchange is performed at the visit (prior to or immediately after procedure, and prior to fluorescein angiography if applicable).
- x Collect at the last Week (X) of the study as required per scenarios 2 and 3, Table 3.

									Weel	k Visit					
Assessment	Screening a	Rand. b	D1 °	4	8	12	16	20	24	28	32	36	40	44	48
Visit window (days)	≥21 days from prior ITV Anti-VEGF Tx	21–27 days from last ITV RBZ Tx	NA						±	:7					
Informed consent	x d														
Review of inclusion and exclusion criteria	х														
Medical and surgical history	х														
Demographic data	х														
Height and Weight	х														
Contact IxRS	х	х		х	х	х	х	х	х	х	х	х	х	х	х
Vital signs e	х	х													
Concomitant medications f	х	х		х	х	х	х	х	х	х	х	х	х	х	х
Adverse event g			х	х	х	х	х	х	х	х	х	х	х	х	х
Concurrent ocular procedures h	х	х	х	x	х	х	х	х	х	х	х	х	х	x	х

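### Protocol Section 5.1.5.3 bars supplemental ranibizumab outside eight listed visits, while Appendix 5 and Appendix 1 Table 3 also provide for it at Weeks 112 and 116

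*Protocol*

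**What the plan says.** **Section 5.1.5.3 of the protocol** makes implant-arm patients eligible for a supplemental 0.5 mg injection at Weeks 16, 20, 40, 44, 64, 68, 88 and 92 if any of three vision or thickness criteria is met. The Note repeats the list and closes it: "Supplemental treatment is not allowed at any other study visits". It makes no exception for patients who stay beyond Week 96 and does not refer to the alternate schedules.

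**Appendix 5** sets out what to do when the criteria are met, including the injection itself. It names the same eight weeks and also "Weeks 112 and 116 for patients who follow an alternate final study visit scenario".

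**Appendix 1 Table 3**, the implant-arm schedule for alternate final visits, has a row beginning "Supplemental ranibizumab (if supplemental treatment criteria are met", marked in the Week (X) column. Footnote u restricts it: "Only for patients who will reach Week 112 and 116". The footnote then refers to Appendix 5.

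**Figure 1 of the protocol**, footnote a, describes implant patients as possibly "eligible for supplemental treatment with intravitreal ranibizumab 0.5 mg at Weeks 16, 20, 40, 44, 64, 68, 88, and 92". It contains no bar. Footnote b tells sites with patients who cannot finish and enrol in the extension study (Portal) on the same day to "follow the alternate scenarios presented in Table 3 and the schedules of activities in Appendix 1, Table 3 and Appendix 2, Table 3".

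**The SAP** repeats the eight-week list in its Figure 1 footnote a and in Section 2.

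**The concern.** Both texts are current and operative. A site running a Week 112 or Week 116 visit would work from Appendix 1 Table 3, see the supplemental row and go to Appendix 5. Appendix 5 refers back to Section 5.1.5.3 for the criteria, and the Note there forbids the injection at that visit. The cross-references therefore lead from the permission to the prohibition.

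At stake is whether an implant patient with a worsening study eye receives the rescue that the schedule provides. A site that follows the Note could withhold the injection or log it as a protocol deviation. Section 5.1.5.3 also provides for stopping study treatment when a patient needs study-eye treatment outside the protocol. That step is not automatic: it depends on the investigator's judgment and a discussion with the Medical Monitor.

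**Working it through.** No sample size, power or alpha figure is involved. The check compares the visit lists and tests whether the two added weeks fit the plan's timing rule.

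**1. Difference between the lists**

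- Section 5.1.5.3: {16, 20, 40, 44, 64, 68, 88, 92}, 8 visits.
- Appendix 5: the same 8 plus {112, 116}, so 8 + 2 = 10 visits.
- Difference: exactly {112, 116}, the two weeks named in Appendix 1 Table 3 footnote u.

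**2. Do the added weeks fit the timing rule?** SAP Section 4.4.2 places the eligible visits 8 and 4 weeks before each scheduled refill.

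| Refill week | Earlier visit | Later visit |
|---|---|---|
| 24 | 24 − 16 = 8 | 24 − 20 = 4 |
| 48 | 48 − 40 = 8 | 48 − 44 = 4 |
| 72 | 72 − 64 = 8 | 72 − 68 = 4 |
| 96 | 96 − 88 = 8 | 96 − 92 = 4 |
| 120 (assumed) | 120 − 112 = 8 | 120 − 116 = 4 |

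All ten visits fit. The Week 120 refill is an assumption: 96 + 24 = 120 on a schedule counted from Day 1. No table lists it.

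**3. Weeks since the last refill**

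- Scenario 2 of Protocol Table 3 (Section 3.1) says "Conduct the Week 96 visit and administer a PDS refill-exchange". Then 112 − 96 = 16 and 116 − 96 = 20, the spacing of the earlier intervals.
- Scenario 3 (Week 96 missed, refill at the first Week (X) visit conducted): if that is Week 100, 112 − 100 = 12 and 116 − 100 = 16; if Week 104, 112 − 104 = 8 and 116 − 104 = 12. The 16/20-week spacing does not hold here.

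**4. Who is affected?** Scenario 1 ends at Week 100. Only implant patients in scenarios 2 or 3 who are still in the study at Week 112 or later can meet the conflict.

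**5. Which text is intended?** Section 3.1 says that Archway patients should in general be able to "remain on study and receive treatment at regular intervals until consenting patients can enroll into Portal per-protocol". That supports the appendices, as does step 2. For the intravitreal arm, Section 4.3.2.2 does point to Appendix 2 Table 3 for injections after Week 92. Section 5.1.5.3 has no matching pointer for the implant arm, so an omission is the likeliest explanation.

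**6. Which analyses are affected?** SAP Section 4.4.2 uses no data after Week 96 for the visual acuity endpoints, and SAP Section 4.7 puts post-Week 96 safety data in a listing only. SAP Section 4.4.2 also summarises supplemental treatment over the whole study period. SAP Section 2.3 equates the 2-year study period with Week 96, so on that reading Weeks 112 and 116 fall outside, although Section 4.4.2 does not say so for this proportion.

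**The case against.** The best defence is that the protocol already sends these patients to the appendix. Figure 1 footnote b does so, and so does footnote cc of Appendix 1 Table 2. The synopsis allows for additional study treatments until a patient can enter the long-term study. Section 5.1.5.3 can also be read as covering the base schedule only. It mentions refills at Weeks 24, 48 and 72 but not the Week 96 or Week (X) refills that Protocol Table 3 permits, and its example of treatment outside the protocol is Week 8. On this reading the specific appendix supplements a general rule.

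This is good evidence of intent, and it is why the appendices should stand. It does not resolve the conflict. None of these pointers states precedence, and the bar in the Note is unqualified.

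Four further points have some force:

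- **Harm is not shown.** Eligibility is assessed through the interactive response system, and the documents do not say how it was set up for Weeks 112 and 116. Withheld rescue is therefore a possibility, not a demonstrated event.
- **Discontinuation is doubtful.** An injection given under Appendix 5 is provided for in the protocol, so the discontinuation sentence may not apply to it.
- **The Week 120 refill is inferred.** The argument from timing must be read with that in mind.
- **The SAP edits change no analysis.** SAP Section 2 is a design summary that defers to the protocol, so edits there are for consistency only.

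**Conclusion.** The inconsistency is real and minor. Section 5.1.5.3 is wrong as written for implant patients in the extended scenarios: it forbids an injection that Appendix 5 and Appendix 1 Table 3 provide for. The bar appears only in Section 5.1.5.3. The Figure 1 footnote and the two SAP lists are merely incomplete.

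The size is two visits (10 against 8), for an unstated and possibly zero number of patients. The primary endpoint at Weeks 36 and 40 and the visual acuity endpoints to Week 96 are untouched.

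That the texts conflict rests on their wording alone and needs no assumption. The view that the appendices are the intended rule is an inference from the assumed Week 120 refill, the Section 3.1 statement on continued treatment and the references to Appendix 1 Table 3.

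**What to change.** In Protocol Section 5.1.5.3, add "Weeks 112 and 116 for patients who follow an alternate final study visit scenario" to the list in the eligibility sentence and to the list in the Note, so that the bar on other visits follows a complete list. Appendix 5 and Appendix 1 Table 3 need no change.

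For consistency only, add the same phrase to Protocol Figure 1 footnote a, SAP Figure 1 footnote a and the list in SAP Section 2.

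The cost is one phrase in two places, plus three optional consistency edits. Because the change concerns permitted treatment, it would need ethics approval before implementation under Protocol Section 9.7. Data collection, sample size and the analyses to Week 96 do not change.
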